4.2.13.2 Derivations

Three items selected from the PROMIS physical function item bank will be used in this study. The items capture physical function impacts separate from those related to pain interference.

A total score will be derived by summing up the responses of the three items. Change from baseline to the end of each cycle in PROMIS item and total scores will be derived.

4.2.13.3 Intercurrent Events

Follow the same approach as outlined for the 2nd key secondary endpoint in Section [4.2.2.2.3](#).

4.2.13.4 Handling of Dropouts and Missing Data

Missing items within an assessment will be handled as described in Section [4.2.13.2](#).

4.2.13.5 Primary Analysis of PROMIS Physical Function Items

The primary analysis for PROMIS Physical Function items (including total score) will be similar to the primary analysis of the 2nd key secondary endpoint as described in Section [4.2.2.2.5](#), that is, the PROMIS item/total score change from baseline at each cycle during the randomised period will be compared between study intervention arms using an MMRM with treatment, geographical region, average baseline chronic target PN pain intensity group and cycle number as factors as well as baseline PROMIS item/total score as a covariate.

Adjusted mean changes from baseline estimates per treatment group over the randomised period of study treatment and at each cycle up to Cycle 12 are presented along with 95% CIs. The corresponding treatment differences, 95% CIs, and p-values are also presented.

The analysis will be performed on a subset of the FAS population with an evaluable baseline assessment and at least one evaluable post-baseline assessment. An evaluable assessment is defined as a PROMIS Physical Function item/total score. Data collected during the randomised period (see Section [3.3.2.2](#)) adhering to the intercurrent event strategy (refer to Section [4.2.13.3](#)) are included.

4.2.13.6 Additional Analyses of PROMIS Physical Function Items

PROMIS Physical Function actual item/total scores as well as the change from baseline at each cycle will be summarised descriptively by study intervention arm. If there are instances of early crossover, then some cycles prior to Cycle 12 will summarise data of placebo subjects who have already crossed over to selumetinib. Plots of the mean scores, as well as change from baseline, and associated 95% CI by cycle will be produced for the randomised period.

The analysis will be performed on the FAS and the Pain FAS.

4.2.14 Paediatric Quality of Life Inventory NF1 Module – Adult Form

4.2.14.1 Definition

The adult version of the Paediatric Quality of Life Inventory (PedsQL) NF1 Module can be used to understand the multidimensional nature of NF1 on the HRQoL patients with this disorder and may assist in medical decision making. The instrument demonstrates initial feasibility, reliability, and discriminant validity. The PedsQL NF1 Module 3.0: Adult self-report instrument comprises 18 domains/subscales and patients will be assessed using the Skin Sensations domain (3 items).

The PedsQL questionnaire is planned to be collected at Baseline, Cycles 2, 4, 8, and 12 during the randomised period as well as at Cycles 16, 20, 24, 30, and every 6 cycles onwards as per the Schedule of Activities (see Section 1.3 of the CSP).

The randomised period is defined in Section [3.3.2.2](#).

4.2.14.2 Derivations

Items are rated on a 5-point Likert scale from 0 (“Never”) to 4 (“Almost always”). Items are reverse-scored and linearly transformed to a 0 to 100 scale as follows: 0 = 100, 1 = 75, 2 = 50, 3 = 25, 4 = 0. Domain scores are calculated by the sum of all the items over the number of items answered. If more than 50% of the items in the scale are missing, the scale score should not be computed. If 50% or more items are completed, missing scores will then be imputed with the mean of the completed items in a scale.

The change from baseline to the end of each cycle in the PedsQL Skin Sensation domain score will be derived.

4.2.14.3 Intercurrent Events

Follow the same approach as outlined for the 2nd key secondary endpoint in Section [4.2.2.2.3](#).

4.2.14.4 Handling of Dropouts and Missing Data

Missing items within an assessment will be handled as described in Section [4.2.14.2](#).

4.2.14.5 Primary Analysis of PedsQL (NF1 Module – Adult Form)

The primary analysis for the PedsQL Skin Sensations domain score will be similar to the primary analysis of the 2nd key secondary endpoint as described in Section [4.2.2.2.5](#), that is, the PedsQL Skin Sensations domain score change from baseline at each cycle during the randomised period will be compared between study intervention arms using an MMRM with treatment, geographical region, average baseline chronic target PN pain intensity group and cycle number as factors as well as baseline PedsQL Skin Sensations domain score as a covariate.

Adjusted mean change from baseline estimates per treatment group over the randomised period of study treatment and at each cycle up to Cycle 12 are presented, along with 95% CIs. The corresponding treatment differences, 95% CIs, and p-values are also presented.

The analysis will be performed on a subset of the FAS population with an evaluable baseline assessment and at least one evaluable post-baseline assessment. Evaluable assessment is defined as a PedsQL Skin Sensations domain score. Data collected during the randomised period (see Section 3.3.2.2) adhering to the intercurrent event strategy (refer to Section 4.2.15.3) are included.

4.2.14.6 Additional Analyses of PedsQL (NF1 Module – Adult Form)

The PedsQL Skin Sensations domain actual scores as well as the change from baseline at each cycle will be summarised descriptively by study intervention arm. If there are instances of early crossover, then some cycles prior to Cycle 12 will summarise data of placebo subjects who have already crossed over to selumetinib. Summary statistics will include n, mean, standard deviation, min, Q1, median, Q3, and max. Graphical plots of the mean scores as well as change from baseline and associated 95% CIs by cycle will be produced for the randomised period.

The analysis will be performed on the FAS and the Pain FAS

4.2.15 EuroQoL Five Dimensions, Five Level Health State Utility Index

4.2.15.1 Definition

The EuroQoL five dimensions, five level health state utility index (EQ-5D-5L) will be used to explore the impact of treatment and disease state on health state utility.

The EQ-5D-5L, developed by the EuroQoL Group, is a generic questionnaire that provides a simple descriptive profile of health and a single index value for health status for economic appraisal (EuroQoL 2019). The EQ-5D-5L questionnaire comprises 6 questions that cover 5 dimensions of health (mobility, self-care, usual activities, pain/discomfort, and anxiety/depression) over 5 levels of increasing severity (“no problems,” “slight problems,” “moderate problems,” “severe problems,” and “extreme problems”). Patients indicate their current health state by selecting the most appropriate level in each of the 5 dimensions.

Respondents also assess their health today using the EQ-VAS, which ranges from 0 (worst imaginable health) to 100 (best imaginable health).

The EQ-5D-5L questionnaire is planned to be collected at baseline and at Cycles 2, 4, 8, and 12 during the randomised period as well as at Cycles 16, 20, 24, 30, and every 6 cycles onwards, as per the Schedule of Activities (see Section 1.3 of the CSP).

The randomised period is defined in Section [3.3.2.2](#).

4.2.15.2 Derivations

A unique EQ-5D-5L health state, termed the EQ-5D-5L profile, is reported as a five-digit code with a possible 3,125 health states. For example, state 11111 indicates no problems on any of the five dimensions. Respondents also assess their health today using the EQ-VAS, which ranges from 0 (worst imaginable health) to 100 (best imaginable health).

The EQ-5D profile will be converted into a weighted health state utility value, termed the EQ-5D index, by applying a country-specific equation to the EQ-5D-5L profile that represents the comparative value of health states. This equation is based on national valuation sets elicited from the general population, and the base case will be the United Kingdom perspective. Where a valuation set has not been published, the EQ-5D-5L profile will be converted to the EQ-5D index using a crosswalk algorithm (

[Van Hout et al](#)).

The EQ-VAS is reported separately. No derivation is needed for the EQ-VAS.

4.2.15.3 Intercurrent Events

Follow the same approach as outlined for the 2nd key secondary endpoint in Section [4.2.2.2.3](#).

4.2.15.4 Handling of Dropouts and Missing Data

Missing cycle assessments will not be imputed, that is, only observed data will be used for this analysis.

4.2.15.5 Primary Analysis of EQ-5D-5L

The primary analysis for EQ-5D-5L total score will be similar to the primary analysis of the 2nd key secondary endpoint as described in Section 4.2.2.2.5, that is, the EQ-5D-5L total score change from baseline at each cycle during the randomised period will be compared between study intervention arms using an MMRM with treatment, geographical region, average baseline chronic target PN pain intensity group and cycle number as factors as well as baseline EQ-5D-5L total score as a covariate and baseline EQ-5D-5L total score-by-cycle and treatment-by-cycle as interactions.

The adjusted mean changes from baseline estimates per treatment group over the randomised period of study treatment and at each cycle up to Cycle 12 are presented, along with 95% CIs. The corresponding treatment differences, 95% CIs, and p-values are also presented. A plot of the LS means accompanied by the 95% CI will be produced.

The analysis will be performed on a subset of the FAS population with an evaluable baseline assessment and at least one evaluable post-baseline assessment. An evaluable assessment is defined as an EQ-5D-5L total score. Data collected during the randomised period (see Section 3.3.2.2) adhering to the intercurrent event strategy (refer to Section 4.2.15.3) are included.

The above analysis will be repeated for EQ-VAS.

4.2.15.6 Additional Analyses of EQ-5D-5L

Summary statistics (eg, n, mean, standard deviation, min, Q1, median, Q3, and max) will be reported for the EQ-5D index score and the EQ-VAS score, and the change from baseline for the EQ-5D index score and the EQ-VAS score. If there are instances of early crossover, then some cycles prior to Cycle 12 will summarise data of placebo subjects who have already crossed over to selumetinib.

The analysis will be performed on the FAS.

To support submissions to payers, additional analyses may be undertaken, and these will be outlined in a separate Payer Analysis Plan.

4.2.16 PFS During the Randomised Period

4.2.16.1 Definition

If the data show evidence of early progression, then the PFS during the Randomised Period will be analysed. Evidence of early progression will be defined as at least 5 events of progression or death due to any cause during the Randomised Period over both treatment groups.

The randomised period is defined in Section 3.3.2.2, and PFS is defined in Section 4.2.5.

4.2.16.2 Derivations

PFS will be derived using the while on-treatment MRI volumetric assessments (see Section 3.3.2.1).

The 2-missed-visit rule as described in the PFS section is not applicable for this analysis.

4.2.16.3 Primary Analysis of PFS During the Randomised Period

A KM plot of PFS will be presented. The percentage of PFS at Months 4, 6, 8, 10, and 11 will be summarised based on the KM method. If more than 50% of patients progress in either arm, the median PFS and 95% CIs will also be calculated using the KM method and presented in the summary table.

Data will be summarised and analysed using the FAS.

4.2.16.4 Additional Analyses of PFS During the Randomised Period

PFS will be calculated based on all on-treatment MRI volumetric assessments without excluding scans during study intervention interruption. The analysis will follow the same methods as the primary analysis of PFS during the randomised period.

4.2.17 PAINS-pNF Spike Target PN Pain Intensity

4.2.17.1 Definition

The primary definition will be the patient's mean maximum cycle score in PAINS-pNF spike target PN pain intensity at each cycle and will be assessed amongst all randomised patients. This definition will exclude cycles for which the patient's maximum score was 0 or missing and will not interpolate for these.

4.2.17.2 Derivations

The baseline PAINS-pNF spike target PN pain score is defined as the maximum PAINS-pNF spike target PN pain score over the screening period, regardless of the number of missing scores in the screening period.

The maximum cycle PAINS-pNF spike target PN pain score is defined as the maximum PAINS-pNF spike target PN pain score over the 28 days up to and including the last day of the cycle, regardless of the number of missing scores in the 28 days.

For the spike pain definition, cycles where the patients' maximum score is 0 for spike pain will be excluded.

At each cycle, the PAINS-pNF spike target PN pain score change from baseline is defined as the cycle PAINS-pNF spike target PN pain score at the specific cycle minus the baseline PAINS-pNF spike target PN pain score. The randomised period is defined in Section [3.3.2.2](#).

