4.2.2.1.2 Derivations

The response variable for a cycle will be the average cycle PAINS-pNF chronic target PN pain score change from baseline, defined as the average of the available daily PAINS-pNF chronic target PN pain scores for the 28 days up to and including the last day of the cycle minus the baseline PAINS-pNF chronic target PN pain score.

The average cycle PAINS-pNF chronic target PN pain score will only be derived if the patient meets the criteria of having at least 4 daily pain scores in at least 3 non-overlapping 7-day periods in the 28-day cycle. Baseline PAINS-pNF chronic target PN pain is defined as the average of the available daily PAINS-pNF chronic target PN pain scores in the screening period. During this time, patients must complete their pain diary for at least 4 days in at least 2 non-overlapping 7-day periods in order to determine the patient's average baseline chronic target PN pain intensity score.

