4.2.17.3 Handling of Dropouts and Missing Data

Missing PAINS-pNF data after treatment discontinuation is handled by the “while on-treatment” approach, using the PAINS-pNF of cycles where a patient was on treatment.

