4.2.17.4 Primary Analysis of PAINS-pNF Spike Target PN Pain Intensity

The primary analysis for PAINS-pNF spike target PN pain intensity score will mirror the primary analysis of the 2nd key secondary endpoint, as described in Section [4.2.2.5](#), that is, the maximum score during the randomised period will be compared between arms using an MMRM model with treatment and geographical region as factors as well as baseline spike pain intensity score as a covariate and baseline spike pain intensity score-by-cycle and treatment-by-cycle as interactions. The LS mean (95% CI) in each study intervention arm as well as the treatment difference and p-value will be presented at each cycle and

overall, in the randomised period. A plot of the LS means accompanied by the 95% CI will be produced.

The analysis will be performed on the FAS population with a baseline score and at least one post-baseline assessment for spike target PN pain intensity.

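### Spike pain is scored as a maximum with no minimum number of diary days, so short or sparsely completed cycles read low

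*SAP*

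**What the plan says.** SAP 4.2.17.2 defines the cycle spike score as the highest daily score in the 28 days to the end of the cycle, "regardless of the number of missing scores in the 28 days". Baseline is the "maximum PAINS-pNF spike target PN pain score over the screening period, regardless of the number of missing scores in the screening period". One diary entry is therefore enough for either value.

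The only filter concerns zeros: "This definition will exclude cycles for which the patient's maximum score was 0 or missing" (SAP 4.2.17.1). The analysis set is the FAS "with a baseline score and at least one post-baseline assessment for spike target PN pain intensity", and "the maximum score during the randomised period will be compared between arms using an MMRM model" (both SAP 4.2.17.4). The listed model terms are treatment, region, baseline spike score and interactions with cycle; none reflects the number of diary days. Estimates, confidence intervals and p-values are planned at each cycle and overall. The additional analyses (SAP 4.2.17.5) are descriptive and include no completeness check.

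The chronic-pain item, from the same daily diary, is treated differently. Its cycle average is derived only for a patient "having at least 4 daily pain scores in at least 3 non-overlapping 7-day periods in the 28-day cycle" (SAP 4.2.2.1.2), its baseline needs at least 4 scores in at least 2 such periods, and SAP 4.2.2.1.6 tests three alternative completeness rules.

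**The concern.** The expected maximum rises with the number of days observed, so the score reflects diary completion as well as pain. A mean, as used for chronic pain, does not depend on the number of days in that direct way. The stricter rule is therefore attached to the summary that needs it less.

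The plan itself produces short records. PRO collection stops once study intervention is discontinued (Protocol 8.1.8), and the spike analysis proceeds by "using the PAINS-pNF of cycles where a patient was on treatment" (SAP 4.2.17.3), so the days before stopping can still yield a cycle maximum. The endpoint table in SAP 4.2 assigns spike pain the intercurrent-event strategy of the first key secondary endpoint. Under SAP Table 9, scores after the first 28 days of a prolonged interruption are excluded until dosing restarts, so a cycle at either edge of that gap can be partial.

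Protocol Table 3 anticipates selumetinib interruptions for several toxicities. If the selumetinib arm had more short or sparse cycles, its maxima would be lower for the same pain, and the comparison would lean towards the drug.

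**Working it through.** The documents give no power or sample-size figure for spike pain, so there is nothing to reproduce. The check covers direction, size per record and size between arms.

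**Direction.** For one patient, the maximum over a subset of days is at most the maximum over all days. This needs no assumption. For independent days with distribution F, P(max ≤ x) = F(x)^n, which shifts upward as n grows.

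**Inputs.** From the documents: a 0-10 integer scale (Protocol 8.1.8.1), 28-day cycles, no minimum number of spike entries, and cycles with maximum 0 dropped. Assumed, because the documents give no daily spike distribution:

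- Model A: a score every day; person mean 4, between-person SD 1.5, within-person SD 2, rounded and limited to 0-10.
- Model B: spikes on 30% of days, severity mean 5 and SD 2, zero cycles dropped.
- Variants: another severity distribution with mean 5, day-to-day correlation 0.8, and patients differing in spike frequency and severity.

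**Size per record, no treatment effect.** Model A mean maximum: 5.68 (3 days), 6.67 (7), 6.80 (8), 7.20 (12), 7.34 (14), 7.91 (28). A 7-day record is 7.91 − 6.67 = 1.24 below a full cycle.

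Four days against 28 days:

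| Assumption | 4 days | 28 days | Gap |
|---|---|---|---|
| Model B | 5.58 | 7.81 | 2.23 |
| 30% of days, other severity distribution | 5.43 | 7.10 | 1.67 |
| Correlation 0.8 | 4.63 | 5.95 | 1.32 |
| Patients differ | 5.57 | 6.62 | 1.05 |
| Patients differ, frequency and severity linked | 6.20 | 6.86 | 0.66 |

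The gap runs from about 0.7 to 2.2 points and never reverses. Dropping zero cycles weakens the effect but makes inclusion depend on diary days: with spikes on 10% of days, a 4-day record has maximum 0 with probability 0.9^4 = 66%, a 28-day record with 0.9^28 = 5%.

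**Size between arms, same pain in both.**

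- Completion 90% against 80%: about 0.1 points.
- Completion 90% against 60%: 6.81 − 6.64 = 0.17 when patients differ and zero cycles are dropped, about 0.3 in Model A, and about 0.5 with intermittent spikes.
- Discontinuation of 20% in one arm and none in the other, spread evenly over 12 cycles, unstructured-covariance likelihood fit: no more than about 0.07 in Model A and about 0.02 with intermittent spikes. Each such patient contributes one truncated cycle; later cycles are missing.

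**Baseline.** The documented floor of 4 × 2 = 8 diary days is an eligibility rule for the chronic item (Protocol 5.1, criterion 3); none is stated for spike. In Model A an 8-day baseline against a 28-day cycle shows 7.91 − 6.80 = 1.11 points of apparent worsening with no true change.

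**Effect of the completeness rule.** The sparsest cycle allowed has 4 × 3 = 12 days. Its gap to a full cycle is 7.91 − 7.20 = 0.71 in Model A, against 7.91 − 5.68 = 2.23 for a 3-day record. With the other severity distribution the gap falls from 1.67 (4 days) to 7.10 − 6.31 = 0.79.

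**The case against.** A reader might infer that the rule hands selumetinib a false benefit of about 1 point. The documents do not support that. The 1-point figure compares two records of different length; an arm difference needs unequal completeness, and nothing in the plan shows that there will be any. Other points on this side are also sound:

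- Scores in the first 28 days of an interruption are kept (SAP Table 9) and the diary runs to end of treatment, so an interruption does not in itself reduce entries. Only cycles at the edges of long interruptions are cut.
- SAP 4.1.1.2 tabulates spike diary completion by cycle and arm, and Protocol 8.1.8.9 provides reminders and flags compliance at or below 85%. A marked imbalance would be visible.
- It is tempting to read the baseline artefact into the treatment effect. The MMRM compares the maximum itself with baseline as a covariate, and a short screening record precedes treatment and affects both arms alike. Screening may also last up to 28 days.
- Peak intensity is a legitimate summary of an episodic symptom, and a completeness rule discards some observed spikes.

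These points limit the size. They do not supply a missing safeguard: the completion table shows an imbalance but changes no estimate, and no planned spike analysis restricts on completeness.

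**Conclusion.** The point holds at a modest size. Spike maxima fall as diary days fall, and nothing in the derivation or the model accounts for it. The direction for a given patient is certain; the sizes rest on assumed daily scores. A reasonable range for the false arm difference is 0.1 to 0.5 points for completion gaps of 10 to 30 percentage points, below 0.1 from discontinuation alone, and zero if completeness is equal. For scale, the trial counts a 2-point fall in the chronic score towards pain palliation. The baseline artefact belongs mainly to the descriptive change summaries. Spike pain is exploratory (Protocol Section 3; SAP 4.2) and outside the multiple testing procedure (SAP 3.3.7), so the primary and key secondary conclusions are untouched. The change is still worth making, because p-values are planned at every cycle and the remedy is already written elsewhere in the SAP.

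**What to change.** In SAP 4.2.17.2, derive the cycle spike maximum only when the chronic-item rule is met (at least 4 daily scores in at least 3 non-overlapping 7-day periods), and the baseline maximum only with at least 4 scores in at least 2 such periods. Keep the unrestricted maximum as a sensitivity analysis. At the least, leave the derivation as it is and add the completeness-restricted version as the sensitivity analysis.

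This removes very short records but leaves some dependence on diary days between 12 and 28. Averaging weekly maxima would not cure that: with scattered missing days a week of 4 entries still reads lower than a week of 7, and with intermittent spikes and 90% against 60% completion the gap was 0.64, against 0.50 for the plain maximum.

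The cost is SAP wording and one derivation, with no new data. Some sparse cycles become missing, including a few in which a spike was recorded.
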